# **Efficacy of mirabegron for treatment of nocturnal enuresis in children**

## **Introduction**

Enuresis is an extremely common condition, which, although somatically benign, poses long-term psychosocial risks if untreated.

Nocturnal enuresis (NE) or bedwetting is defined as the voluntary or involuntary wetting of clothes or bedding with urine for a period of at least 3 consecutive months in children older than 5 years of age. It affects 15% - 20% of children aged 5 years, and 1% - 2% of adolescents[2]. Although spontaneous recovery occurs at a rate of 10–15% per year[3], NE still has a certain impact on the child's social, emotional and psychological development. According to the International Children's Continence Society (ICCS) recommendation, NE can be subclassified into monosymptomatic nocturnal enuresis (MNE) and non-monosymptomatic nocturnal enuresis (NMNE) based on whether accompanied with lower urinary tract symptoms (LUTS) or not[4]. MNE is defined as involuntary urine voiding during sleep without other LUTS, such as daytime urinary frequency, urgency, or incontinence of urine. More than 68.5% of NE patients are MNE[5].

Various interventions including pharmacological, behavioral and other approaches have been used for the treatment of MNE. Alarm therapy, one of the first line treatment, has been proved to be effective for MNE and should be first taken into consideration in children under 8 year age with adequate family support[6].

Desmopressin is the most widely used medical treatment in the management of MNE[7]. Combine therapy of desmopressin plus anticholinergics is often taken

into consideration when the patients are refractory to single treatment, having behavioral problems or frequent nighttime enuresis[8].

## **Aim**

To evaluate the efficacy of B3 agonist mirabegron in the management of nocturnal enuresis in children.

## **Patients &Methods:**

The study will be conducted in urology department, Menoufia University Hospital.

**Sample size: 151**

### **Inclusion criteria:**

Children from 5-15 years old

Nocturnal enuresis

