#### **Radiological investigation:**

## Ultrasound abdomen and pelvis

The main outcomes included complete response rate, success rate, mean number of wet nights per week at the end of treatment, relapse rate at the end of following up, and adverse events during the treatment. According to the definition of ICCS, the outcomes were evaluated as follows: (1) complete response (CR) as a 100 % decrease; (2) response (R) as a  $\geq 90$  % decrease; (3) partial response (PR) as a 50–89 % decrease; (4) non-response (NR) as 0–49 % decrease in the number of wet nights. Relapse was defined as reappearance of  $>1$  wet night per week for complete responders or  $>50\%$  of pretreatment wetting frequency for partial responders. CR, R, and PR were regarded as the success.

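### With no minimum wetting frequency at entry, a full return to one wet night a week is a relapse for a partial responder but not for a complete responder

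*Protocol*

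**What the plan says.** The Protocol's Inclusion criteria have two lines: "Children from 5-15 years old" and "Nocturnal enuresis". The Introduction defines the condition as "wetting of clothes or bedding with urine for a period of at least 3 consecutive months in children older than 5 years of age". That gives a duration and an age, but no frequency. The Exclusion criteria add no frequency floor. The Preintervention assessment lists urine tests and an ultrasound, with no baseline count of wet nights.

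The outcomes paragraph is printed under the heading Ultrasound abdomen and pelvis. It grades response by percentage fall in wet nights: "complete response (CR) as a 100 % decrease", response at 90% or more, partial response at 50–89%, non-response below that. It adds that "CR, R, and PR were regarded as the success". The relapse sentence opens "Relapse was defined as reappearance of" and then uses two different scales. For complete responders the threshold is absolute, more than 1 wet night per week. For partial responders it is relative, more than 50% of the pretreatment frequency. Complete response, success and relapse rates are all listed among the main outcomes. No period for counting wet nights is given, before or after treatment.

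**The concern.** Percentage grades and an absolute relapse threshold of more than 1 night per week both presuppose a child who wets well above once a week. Entry does not ensure that. For a child at or below 1 night per week, two things go wrong.

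- Complete loss of effect is classified in opposite ways, depending on whether the child was first graded a complete or a partial responder.
- A 100% fall can be reached through ordinary night-to-night variation if the count is short.

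Three main outcomes (complete response, success, relapse) then depend partly on how many infrequent wetters happen to be enrolled. The first problem lies in the wording of a stated rule. The second depends on details that the Protocol does not give.

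**Working it through.** The Protocol has no figure to reproduce here. The sample size of 151 is given without inputs, and it enters below only to set the scale.

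**1. The two relapse rules side by side.** Let b be the pretreatment wet nights per week. A complete responder relapses above 1 per week, a partial responder above 0.5 × b.

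| b | Complete responder relapses above | Partial responder relapses above | Full return to b: complete responder | Full return to b: partial responder |
|---|---|---|---|---|
| 1 | 1 | 0.5 | not a relapse | relapse |
| 2 | 1 | 1 | relapse | relapse |
| 4 | 1 | 2 | relapse | relapse |

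A full return is missed for complete responders whenever b ≤ 1. The rules coincide at b = 2, since 0.5 × 2 = 1. Below that, the absolute rule is the more lenient of the two; above it, the stricter.

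The contrast can arise in practice once wet nights are counted over two weeks or more. With b = 1, a fall from 2 nights in two weeks to 1, or from 4 nights in four weeks to 2, is a 50% decrease and hence a partial response. With a one-week count, a child with one wet night can only stay the same or reach zero. This step needs no distributional assumption.

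**2. Chance response with no drug effect.** Assumptions: independent nights, constant true rate r per week, nightly probability p = r/7, and a window of w weeks with w = 1, 2 or 4 (assumed, because none is stated).

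Chance complete response = (1 − p)^(7w). For r = 1:

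- one week: (6/7)^7 = 0.340
- two weeks: (6/7)^14 = 0.116
- four weeks: (6/7)^28 = 0.013

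Chance success is the probability that the end count is at most half the baseline count, with both counts binomial(7w, p) over the same window and the baseline count at least 1.

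| True rate per week | Chance complete response, 1 / 2 / 4 weeks | Chance success, 1 / 2 / 4 weeks |
|---|---|---|
| 1 | 34.0% / 11.6% / 1.3% | 50.1% / 34.7% / 20.5% |
| 2 | 9.5% / 0.9% / 0.01% | 32.1% / 18.1% / 7.7% |
| 3 | 2.0% / 0.04% / about 0 | 20.5% / 9.2% / 2.3% |

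If the baseline rate were instead known without error, chance success at r = 1 would be 34% over one week and 39% over two. The success figures therefore depend on the model.

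If wet nights cluster (beta-binomial, intra-child correlation 0.05 to 0.2), chance complete response at r = 1 becomes 39–52%, 20–38% and 7–27% over one, two and four weeks.

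**3. Scale.** The share of once-weekly wetters is not given. Assume 10% to 30% of 151, about 15 to 45 children. Under independence, expected chance complete responders are:

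- one week: 15.1 × 0.340 = 5.1 to 45.3 × 0.340 = 15.4
- two weeks: 1.7 to 5.2
- four weeks: 0.2 to 0.6

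**4. Relapse under the same model.** At an unchanged rate of 1 per week, P(2 or more wet nights in a given week) = 1 − (6/7)^7 − (6/7)^6 = 1 − 0.340 − 0.397 = 0.264. P(at least one such week) is 1 − 0.7365^4 = 70.6% over 4 weeks and 1 − 0.7365^12 = 97.5% over 12. Read as a four-week mean above 1 (5 or more wet nights in 28), it is 37.1%.

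**The case against.** A reader might infer that once-weekly wetters can never relapse, and so can only raise the response rates and never the relapse rate. The documents do not support that. The variation that yields a chance complete response also yields more than 1 wet night in about a quarter of weeks. If any single week above 1 counts, nearly all such children would relapse within 12 weeks. A child who worsens beyond baseline also meets the rule. What stands is narrower: a return to an average of one night per week or less does not in itself meet the threshold.

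A reader might also infer that the response rates are inflated by a known amount whatever the drug does. That is not supported either. With a four-week count and independent nights, chance complete response at 1 per week is 1.3%. A statistical analysis plan that is not at hand may fix the window. The share of such children has no source in the Protocol. The Protocol states neither a single arm nor a comparator; with a concurrent comparator, chance responses would occur in both arms and would not by themselves create a difference. The mean number of wet nights, also a main outcome, uses no response cut-off.

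Finally, the Aim concerns nocturnal enuresis in children generally, so broad entry is a legitimate choice. That objection holds against insisting on an entry floor. It does not answer the conflict between the relapse rules, which the Protocol itself states.

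**Conclusion.** The point holds in two parts of different strength.

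- **Relapse.** With no entry frequency, the stated rules classify a full return to a baseline of 1 wet night per week as no relapse after complete response and as relapse after partial response. This follows from the text, for any complete responder with a baseline of 1 per week or less. It misclassifies a main outcome and should be corrected.
- **Chance response.** At a true rate of 1 per week, chance complete response is 34%, 12% or 1.3% for one-, two- or four-week counts with independent nights, and higher if nights cluster. With an assumed 10–30% share of the 151 children, that is about 5–15, 2–5 or fewer than 1 child. This part depends on the window, the share and the absence of a comparator, so no single figure for the bias can be given.

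**What to change.** 1. In the outcomes paragraph, extend the relapse rule for complete responders so that wetting above 50% of pretreatment frequency also counts. By the table above, this changes the classification only for children with a baseline below 2 per week. Cost: one line, and a slightly higher relapse rate.
2. As an alternative or in addition, state in the Inclusion criteria a minimum pretreatment wetting frequency above the relapse threshold, with the value set by the investigators. Any floor above 1 per week makes a full return register as relapse; from 2 per week upward the absolute rule is never the more lenient one. Cost: a slightly narrower population and slower recruitment.
3. Count wet nights over the same fixed multi-week window at baseline and at end of treatment, for example four weeks, and say whether relapse is judged on a single week or on a mean over that window. Cost: a baseline diary of that length.

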### **Exclusion criteria:**

Patients with anatomical lower urinary tract abnormalities

Any neurological diseases

Experienced treatment failure

Active urinary tract infection

### **Preintervention assessment:**

#### **Laboratory investigations:**

Urine analysis and urine culture & sensitivity

#### **Radiological investigation:**

## Ultrasound abdomen and pelvis

The main outcomes included complete response rate, success rate, mean number of wet nights per week at the end of treatment, relapse rate at the end of following up, and adverse events during the treatment. According to the definition of ICCS, the outcomes were evaluated as follows: (1) complete response (CR) as a 100 % decrease; (2) response (R) as a  $\geq 90$  % decrease; (3) partial response (PR) as a 50–89 % decrease; (4) non-response (NR) as 0–49 % decrease in the number of wet nights. Relapse was defined as reappearance of  $>1$  wet night per week for complete responders or  $>50\%$  of pretreatment wetting frequency for partial responders. CR, R, and PR were regarded as the success.

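### The safety outcome stops with treatment although children are followed afterwards for relapse, so adverse events that first begin after the last dose fall outside it

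*Protocol*

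**What the plan says.** The only safety text is in the main-outcomes paragraph of the Protocol, printed under the heading *Ultrasound abdomen and pelvis*. It names five main outcomes: complete response rate, success rate, wet nights, relapse and adverse events. The last three each carry a time reference:

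- Wet nights: "mean number of wet nights per week at the end of treatment".
- Relapse and safety, side by side: "relapse rate at the end of following up, and adverse events during the treatment".

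The same paragraph gives the relapse rule, which opens "Relapse was defined as reappearance of" and sets one wetting threshold for complete responders and another for partial responders.

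The Protocol does not state how long treatment or follow-up lasts, gives no period after the last dose in which events are still counted, and does not say how events open at the last dose are handled.

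**The concern.** Adverse events are a main outcome in a trial of children from 5 years of age. The protocol plans to observe at least some of these children after treatment, but it closes the safety outcome when treatment ends. An event that appears after stopping would not enter the outcome even if the family mentions it at a relapse contact. For an event still open at the last dose, the report could say that it occurred but might not say whether or when it resolved.

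This is not simply a detail that can wait for the statistical analysis plan. The protocol states a window, and a later analysis can only use what was asked about and recorded. If the outcome wording guides what is collected, information from after the last dose cannot be recovered at the analysis stage.

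**Working it through.** There is no stated figure to reproduce, so the check is one of wording.

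**Step 1: is there observation after treatment?** The paragraph names the end of treatment and the end of follow-up as different time points. It also defines relapse as wetting that returns after a response. Together these imply contact after the last dose. This is a sound inference, but the protocol does not say so outright and gives no duration.

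**Step 2: does any other text widen the safety window?** The aim, eligibility criteria, preintervention assessment and results sections contain nothing on adverse events. The window in the main-outcomes paragraph stands alone.

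**Step 3: what does that window include and exclude?**

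| Event | In the outcome as worded? | What is lost |
|---|---|---|
| Begins and resolves on treatment | Yes | Nothing |
| Begins on treatment, still open at the last dose | Yes | Later course and resolution are not provided for |
| Begins on treatment and leads the child to stop | Yes | As in the row above |
| First begins after the last dose | No | The event itself |

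Only the last row changes the count. The second and third rows concern completeness of description.

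**Step 4: can the gap be sized?** Let A be the number of children with an event that begins on treatment, B the number whose only event begins afterwards, and n the number treated. The outcome as worded is A/n. Over the whole observed period it would be (A + B)/n, so the difference is B/n. The protocol gives "Sample size: 151" and no event rate, treatment length or follow-up length, so B cannot be derived. If all 151 children are treated and analysed, each such child is worth 1/151 = 0.66 percentage points. That gives the scale per child and is not an estimate of the shortfall.

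**The case against.** The strongest reply is that an on-treatment safety window is a recognised choice. Two outcomes may have two windows without contradiction, and a list of outcomes is not a rule for when recording stops. Handling of ongoing events is often set out in a statistical analysis plan, which is not at hand. Part of this stands: the sentence is not inconsistent, and it does not forbid recording later events. It does fix the outcome, however, and as fixed it leaves out events that begin during planned follow-up.

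Several stronger readings are tempting, and the document does not support them:

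- *Events that persist past the last dose, or that make a child stop, are missed from the rate.* They began on treatment and are counted. Missing resolution data does not lower the rate.
- *Wetting that rebounds above the pretreatment level is lost.* In complete and partial responders it would normally meet the relapse threshold, so it would be recorded, though as efficacy.
- *Existing complaints are not recorded before treatment, so they inflate the event rate.* The listed investigations are "Urine analysis and urine culture & sensitivity" and ultrasound, but this is plainly not the whole pretreatment assessment. The exclusions for neurological disease and earlier treatment failure, and the use of pretreatment wetting frequency, all require a history. The inference rests on silence.
- *A number of affected children can be given.* Any such number would rest entirely on assumed rates.

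A practical objection also stands in part. The relapse rule names complete and partial responders only, so later contact with non-responders or early stoppers is not assured.

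**Conclusion.** The point holds in a limited form. Adverse events that first begin after the last dose are outside the safety outcome, although the same sentence has children followed afterwards for relapse. Events open at the last dose are counted, but nothing provides for recording what becomes of them. The conclusion rests on one inference, that follow-up comes after treatment, which the two named time points and the relapse definition support. No size can be attached to the gap. It is a modest weakness in a stated window. It is worth correcting because it concerns safety in children, and the correction is most useful before data are collected.

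**What to change.** Reword the outcome along these lines: *adverse events from the first dose to the last follow-up contact, reported separately for the on-treatment and post-treatment periods*. Add that events open at the last dose have their outcome recorded at the follow-up contacts already made for relapse.

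The cost is a change of wording and a few questions at those contacts. Some background events unrelated to the drug will be recorded after treatment, and separate reporting of the two periods keeps them from blurring the on-treatment rate. Children who are not followed for relapse, such as non-responders and early stoppers, gain from the change only if they are still in contact with the study. The report should therefore state how many children contributed to the post-treatment period.

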## Results:

The results will be recorded, tabulated, and statistically analyzed.

## Discussion:

The results will be discussed in comparison to those mentioned in the literature.

